10.1.2. Efficacy Assessments during the Postdiscontinuation Period

After patients have discontinued study treatment, they may receive additional anticancer therapy at the discretion of the investigator.

For those patients who discontinue study treatment without objectively measured progressive disease, the investigative sites will continue to monitor patients approximately every 60 days (± 14 days) to evaluate tumor response by the same method used at baseline and throughout the study, until objective progression or the patient starts a new anticancer therapy.

Once a patient has objective progression or starts a new anticancer therapy, they will be followed for OS approximately every 60 days (± 14 days) until death or study completion.

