10.1.4. Secondary Efficacy Endpoints

The secondary time-to-event endpoints are defined in [Table JBAL.10.1](#).

Table JBAL.10.1. Secondary Efficacy Endpoints

Endpoint	Definition
Progression-Free Survival	The time from the date of study enrollment (randomization) to the date of first observation of objective progression or death from any cause, whichever occurs first. For patients who are not known to have died or progressed as of the data-inclusion cut-off date, PFS time will be censored at the date of the last objective progression-free disease assessment prior to the date of any subsequent systematic anticancer therapy.
Progression-Free Survival at 6 months	Number of patients not having objective progression or death at 6 months after the time from date of study enrollment (randomization) estimated from the PFS distribution.
Survival at 12 months	Number of patients alive 12 months after start of treatment, even if they have progressed, estimated from the overall survival distribution

Abbreviation: PFS = progression-free survival.

The use of MRI is mandatory to determine tumor response and to assess when objective progressive disease has occurred (for use in estimating PFS). Recent guidelines have modified the MacDonald criteria and these new guidelines are attached in [Attachment 5](#) and are referred to as the RANO criteria (Wen et al. 2010). The MRI scans will be collected and stored centrally; if necessary, independent review of all or a representative sample of scans may be considered following study completion.

Overall response rate (ORR) is the proportion of patients who achieved a complete response (CR) or partial response (PR) out of all randomly assigned patients.

Based on RANO criteria, a responder is defined by radiographic and clinical criteria (see [Attachment 5](#)). Complete response or PR will be first assessed by radiographic changes as determined by an improvement of the bi-dimensional evaluation of the tumor size. In addition, changes in neurologic function and steroid use will be considered to determine stable disease (SD).

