5.1. Summary of Study Design

Study JBAL is a 3-arm, randomized, multicenter, global, Phase 2 study of LY2157299 monotherapy or LY2157299 plus lomustine therapy compared to lomustine plus LY2152799-matched placebo therapy in patients with relapsed or progressed GB.

CCI [REDACTED] patients will be entered with the aim of randomizing CCI [REDACTED] patients in a CCI [REDACTED] fashion to LY2157299 monotherapy or LY2157299 plus lomustine therapy or lomustine plus LY2152799-matched placebo therapy. Patients and investigators will be blinded to the LY2157299 or placebo assignment for those patients who receive lomustine. One cycle is defined as 28 days in all treatment arms and constitutes 14 days on/14 days off of LY2157299/LY2157299-matched placebo.

[figure not shown]
In Cycle 1, lomustine will be given after LY2157299 or placebo has been given for 7 days (on Day 7 of Cycle 1). After the first dose, lomustine will then be given once every 6 weeks to those patients assigned to either the LY2157299 plus lomustine or lomustine plus placebo treatment groups. The planned treatment with lomustine will be limited to 6 administrations.

Patients will receive treatment until disease progression, death, or discontinuation occurs. Patients will be followed for OS until death or study closure. Tumor assessments will be conducted at baseline (within 28 days before the first dose of study drug or 14 days prior to enrollment) and at the end of every 2 cycles (Day 26 ± 2) thereafter.

The primary comparison for efficacy is to compare OS between the LY2157299 plus lomustine therapy and lomustine plus placebo therapy. Additional endpoints (eg, PFS, response rate) will be estimated.

Further analyses will be carried out to estimate efficacy and safety endpoints for LY2157299 monotherapy and LY2157299 plus lomustine therapy. This secondary analysis will provide an assessment of whether the monotherapy treatment with LY2157299 is as active as lomustine alone. At the same time, this design will offer additional information whether LY2157299 monotherapy has a toxicity profile that warrants further investigation.

CCI [REDACTED] interim assessments are planned:

The planned duration of the study is CCI [REDACTED] in order to follow all patients for OS. Overall survival will be collected for all patients, including those who started other

therapies after discontinuation from study drug treatment.

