6.3. Handling of Dropouts or Missing Data

The number of patients that discontinued early from treatment and the reason for discontinuation will be summarized for each treatment arm. See Sections [6.5](#) and [6.6](#) on the method for handling these patients in the analyses.

The primary method for handling missing time-to-event data will be censoring. See details on censoring for each time-to-event endpoints in [Section 6.10](#).

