6.9. Concomitant Therapy

All medications will be coded to the generic preferred name according to the current World Health Organization (WHO) drug dictionary. All concomitant medications listings will include both the term reported in CRF and the WHO dictionary term for enrolled patients in each arm and if concomitant medication use is due to adverse event (AE), the associated AE will also be listed.

Enzyme-inducing and non-enzyme inducing anti-epileptic drug treatments will be determined retrospectively and indicated in the listings.

Patients with concomitant steroid use will be listed separately by each arm. Dose information including total daily dose and any dose modification at the start of each cycle will be provided in this listing.

Surgery for palliative reasons and carried out prior to discontinuation from study treatment will be captured separately.

Anti-cancer systemic therapy, radiotherapy and surgery that occurs post discontinuation of study treatment is captured separately from concomitant medication as the existence of such therapies can lead to censoring of time to event endpoints. Patients that received post discontinuation therapies will be listed by treatment arms.

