6.10. Efficacy Analyses

The following are definitions of the primary and secondary efficacy endpoints:

Primary Endpoint:

- **Overall Survival (OS) duration** is measured from the date of randomization to the date of death from any cause. For each patient who is not known to have died as of the data-inclusion cut-off date for a particular analysis, OS will be censored for that analysis at the date of last contact prior to the data inclusion cutoff date (contacts considered in the determination of last contact date include AE date, lesion assessment date, visit date, and last known alive date). For OS analysis, death is considered an event.

Secondary Endpoints:

- **Progression-Free Survival (PFS) duration** is measured from the date of study enrollment (randomization) to the date of first observation of objective progression or death from any cause, whichever occurs first. For patients who are not known to have died or progressed as of the data-inclusion cut-off date, PFS time will be censored at the date of the last objective progression-free disease assessment prior to the date of any subsequent systematic anticancer therapy.
- **Progression-Free Survival rate at CCI** is defined as the proportion of patients not having objective progression or death at CCI respectively after the time from date of study enrollment (randomization) estimated from the PFS distribution.
- **Survival rate at 12 months** is defined as the proportion of patients alive 12 months after start of treatment, even if they have progressed, estimated from the overall survival distribution.
- **Overall Response Rate (ORR)** is defined as the proportion of patients who achieved a best overall response of either complete response (CR) or partial response (PR). The overall response rate for each treatment group will be estimated by dividing the total number of confirmed responders by the number of patients who received at least 1 dose of study treatment. Response will be evaluated based on the Response Assessment in Neuro-Oncology (RANO).

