6.10.3. Secondary Efficacy Analyses/Outcomes/Comparisons

A similar Bayesian analysis as described in [Section 6.10.1](#) will also be carried out to provide the hazard rates and ratios including 90% predictive intervals of the HR between LY2157299 monotherapy and lomustine plus placebo therapy and, between LY2157299 plus lomustine therapy and LY2157299 monotherapy.

Additional exploratory analyses using proportional hazards models to control for other factors may be performed, including, but not limited to, adding a covariate indicating the extent of lomustine exposure, PD marker assessment of the tumor tissue, the known influence factors, such as age, PS, and primary or secondary GB and whether patients had poststudy treatment with bevacizumab.

The following secondary efficacy parameters will be summarized for each treatment group:

- PFS distribution parameters and PFS rate
- ORR
- Disease control rate

Progression-free survival (PFS) and PFS rate will be summarized (at **CCI** [REDACTED]) using Kaplan-Meier estimates of the median survival times (including 95% CIs) to inform assumptions for use in future trial planning (Kaplan and Meier 1958). Estimates of HRs

between the 3 arms will also be provided using proportional hazards models. Additional exploratory analyses using proportional hazards models to control for other factors may be performed.

Overall response rate (ORR) and, additionally, disease control rate given the risk of pseudoprogression, will be estimated by dividing the total number of responders ([CR or PR]) or [(CR or PR or SD)] by number of randomly assigned patients in each treatment group. Exact 95% CIs for each treatment arm will also be provided.

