6.10.4. Sensitivity Analyses

Additional analyses may be carried out to judge the influence of any patients who did not meet enrollment criteria but were inadvertently enrolled and continued on treatment after obtaining approval from the sponsor and/or patients who have continued treatment after objective disease progression. A subanalysis will be conducted by excluding such patients to determine their influence on the final study results.

Additional sensitivity analyses may also include the use of different censoring dates in the time-to-event analyses.

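### PFS counts deaths after a switch to new therapy as events although scheduled scans ended at the switch, yet censors living switchers at their last scan before it

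*SAP*

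**What the plan says.** SAP 6.10 and Protocol Table JBAL.10.1 define PFS in the same way. The event is first objective progression or death from any cause, with no exception for deaths after new therapy. Later therapy enters only through the censoring sentence: "For patients who are not known to have died or progressed as of the data-inclusion cut-off date, PFS time will be censored" at the last progression-free assessment "prior to the date of any subsequent systematic anticancer therapy".

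Scheduled scans run at baseline "and at the end of every 2 cycles" on treatment (SAP 5.1). After stopping without progression they run about every 60 days "until objective progression or the patient starts a new anticancer therapy" (Protocol 10.1.2). From then on only survival is followed.

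Three other SAP sections touch the point:

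- 6.3 says "The primary method for handling missing time-to-event data will be censoring" and refers to 6.10 for details.
- 6.9 says of therapies after discontinuation that "the existence of such therapies can lead to censoring of time to event endpoints".
- 6.10.4 says "Additional sensitivity analyses may also include the use of different censoring dates".

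PFS medians and rates are meant "to inform assumptions for use in future trial planning" (SAP 6.10.3), and PFS hazard ratios between the three arms are also estimated.

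**The concern.** Take two patients with a clean scan at month 2 who both switch soon afterwards. One dies at month 15 and has a PFS event at month 15, although nobody was scheduled to look for progression in between. The other is alive at cut-off and is censored at month 2. Every switcher has an outcome under the text, but not a uniform one.

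The first patient matters more for the estimate. Thirteen months without scheduled scans are credited as progression-free time. If such patients are common and live well beyond the usual time to progression, the PFS curve is too high, and a later trial planned on it starts from an optimistic figure.

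The scope of therapies also differs. The censoring sentence covers systemic therapy only (printed as systematic), Protocol 10.1.2 stops scans for any new anticancer therapy, and SAP 6.9 also lists radiotherapy and surgery.

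**Working it through.** The plan states no figure for switchers, so there is none to reproduce. The size below is an illustration.

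**Inputs from the documents.** Lomustine in two earlier trials (Protocol Table JBAL.5.1): median PFS 1.64 months with median OS 7.1 months; median PFS 82 days (about 2.7 months) and 6-month PFS 24% with median OS 9.8 months. Average median OS 8.5 months and minimum follow-up 94 weeks (21.6 months): Protocol 12.1.

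**Assumptions.** Switching shares of 5, 10 and 20%; follow-up uniform from 21.6 to 29.6 months; exponential times; new therapy does not itself change progression. Simulations use 400,000 patients per case, and repeat runs differ by up to about 0.2 points.

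**Step 1: most switchers die before cut-off.** The chance of death by 94 weeks is 1 − 2^(−21.6/m): 88%, 83% and 78% for OS medians m of 7.1, 8.5 and 9.8 months. Most switchers would therefore be events dated at death.

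**Step 2: switching independent of disease.** Let h be the PFS hazard, s the switching hazard, p = s/(h+s) the share switching, and d the death hazard after the switch. If all switchers are dated at death,

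S(t) = e^(−(h+s)t) + [s/(h+s−d)]·[e^(−dt) − e^(−(h+s)t)].

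With true 6-month PFS of 24%, h = −ln(0.24)/6 = 0.2379 (median 2.91 months). With p = 20%, s = 0.0595.

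- Post-switch median 9.8 months (d = 0.0707): 0.168 + 0.2624 × (0.654 − 0.168) = 29.6%. The written rule pulls the living back to before the switch, and simulation then gives 28.0%.
- Post-switch median 1 month (d = 0.693): 0.168 + 0.023 = 19.1% (simulated 19.0%), which is too low.
- d = h: the formula collapses to e^(−ht), the true curve. Break-even is therefore a post-switch median equal to the PFS median: 2.9 months here, 1.64 months if median PFS is 1.64. In that second setting a 2.9-month post-switch median still gives 11.4% against a true 7.9%.

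**Step 3: switching that tracks disease.** The switch falls at 30 to 100% of the time to progression. Death follows progression by an exponential time calibrated to the OS median. Post-switch medians come out at about 5.4 and 7.1 months.

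| 20% switching | True 6-month PFS | As written | All switchers censored |
|---|---|---|---|
| Tracks disease, PFS 1.64, OS 7.1 months | 7.9% | 17.8% | 10.9% |
| Tracks disease, PFS 2.7, OS 9.8 months | 21.4% | 30.9% | 26.6% |
| Independent, true 24%, post-switch 9.8 months | 24.0% | 28.0% | 24.1% |

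Across the cases with long post-switch survival, the excess is about +1 to +2 points at 5% switching, +2 to +5 at 10% and +4 to +10 at 20%.

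**Step 4: where the error comes from.** Keep deaths as events but follow living switchers to cut-off, so that both groups are dated alike. The three cases then go from 17.6 to 18.0%, 30.9 to 31.5% and 27.9 to 29.5%. The excess does not fall, so the dependence on vital status is not its source.

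**Step 5: where censoring loses.** If switching tracks disease and switchers die a median of 0.5 months after progression, the written rule gives 8.6% against 10.7% with censoring (true 7.9%), and 22.4% against 26.7% (true 21.4%). The two rules cross at about 1.3 months in the first setting and 2 months in the second.

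**Step 6: scan-based cross-check.** With 56-day scans, median progression 2.7 months and independent death with median 8.5 months, true 6-month PFS was 15%. The written rule gave 19, 23 and 28% at switching shares of 12, 25 and 37%. Censoring all switchers at the last scan gave 14, 13 and 12%, slightly low.

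**The case against.** **Counting every death is a legitimate definition, and the text leaves nobody unassigned.** Both parts are right. A reader might infer that switchers have no rule at all. They do; it depends on later vital status. But a strategy that counts all deaths would keep scanning after the switch, and would not pull living switchers back to an earlier date.

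**Few patients may be affected.** This stands. RANO (Protocol Attachment 5) counts clinical deterioration and failure to return because of it as progression, and back-dates equivocal scans. Many disease-driven switchers would already be events. Nor does Protocol 10.1.2 bar recording a progression seen after the switch.

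**The error is small beside sampling error.** Arm sizes are redacted. At an assumed 60 per arm, one standard error on 24% is √(0.24 × 0.76/60) = 5.5 points, so at 5 to 10% switching the bias is below one standard error. This supports a low grade, although a bias does not average out.

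**The SAP already allows for it.** Only in part. SAP 6.9 captures the therapies without fixing an endpoint or date, and the alternative dates in 6.10.4 are optional and unnamed.

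**Censoring is not always better.** This stands too (Steps 5 and 6).

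**Conclusion.** The text is inconsistent in its treatment of switchers, and counting unscanned deaths can distort PFS. At assumed switching shares of 5 to 20%, 6-month PFS is too high by about 1 to 10 points when survival after the switch is clearly longer than median PFS. With independent switching it is too low only when the post-switch median is below the PFS median. When switching tracks disease it was not too low in any case run.

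Three stronger readings are not supported:

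- That PFS is always overstated. The direction depends on survival after the switch, which the documents do not give.
- That the comparison between arms is biased. This needs unequal switching. The monotherapy arm is open-label, so unequal switching is possible, but nothing shows it. In the scan-based run with no true difference, equal shares of about 25% gave a hazard ratio of 0.98; shares of 12% in control and 37% in the experimental arm gave 0.82.
- That the main conclusion is at risk. The primary endpoint is OS, which does not use this rule, and PFS has no success criterion.

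The grade is minor. The reading of the text is firm; the size rests on the assumed shares and models.

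**What to change.** In SAP 6.10 and Protocol Table JBAL.10.1, add one sentence: any patient who starts a new anticancer therapy that ends tumour assessment under Protocol 10.1.2, before documented progression, is censored at the last progression-free assessment before that therapy, whether or not the patient later dies. Tying the rule to 10.1.2 also removes the mismatch over systemic therapy.

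In SAP 6.10.4, replace the optional wording with two named analyses:

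- all deaths as events, with living switchers censored at the last known alive date;
- start of new therapy as an event (this fell below the true 6-month PFS in every case run).

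Report the number of switchers without progression per arm, and show both analyses beside the main estimate, since the documents do not establish which rule is least biased.

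The cost is one sentence in two places and two reruns on data already collected. PFS events fall by about the number of switchers who die: about 5 per 100 patients at 5% switching and 18 to 19 per 100 at 20% when switching tracks disease. In that situation some upward bias remains, about 3 to 5 points at 20% (10.9 against 7.9%, 26.6 against 21.4%).

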6.10.1. Primary Outcome and Primary Methodology

Overall survival (OS) is the primary outcome of interest and the definition of OS is as described above.

A method of analysis for comparing OS between the combination arm, LY2157299 plus lomustine therapy and the control arm, lomustine plus placebo therapy will use a Bayesian exponential-likelihood model with possibly a hierarchical random-effects distribution on treatment effects. The model incorporates historical data from 2 studies (Study H6Q-MC-JCBF [data on file and Wick et al. 2010a]; Batchelor et al. 2010a;) with a lomustine plus placebo arm to augment the prospective control arm data. If the Bayesian posterior probability of superiority of LY2157299 plus lomustine therapy over lomustine plus placebo therapy (control) (ie, HR **CCI** [REDACTED]), then it will be concluded that the combination arm is superior.

6.10.2. Additional Analyses of the Primary Outcome

Overall survival (OS) and OS rate at 12 months will be summarized by the combination arm (LY2157299 plus lomustine) and control arm (lomustine plus placebo) using Kaplan-Meier estimates of the median survival times (including 95% CIs) to inform assumptions for use in future trial planning (Kaplan and Meier 1958). Kaplan Meier plots of survival for each treatment group will also be provided.

Additional analyses of overall survival comparing LY2157299 monotherapy and lomustine plus placebo therapy and, between LY2157299 plus lomustine therapy and LY2157299 monotherapy are considered secondary efficacy analyses and described in the following section.

6.10.3. Secondary Efficacy Analyses/Outcomes/Comparisons

A similar Bayesian analysis as described in [Section 6.10.1](#) will also be carried out to provide the hazard rates and ratios including 90% predictive intervals of the HR between LY2157299 monotherapy and lomustine plus placebo therapy and, between LY2157299 plus lomustine therapy and LY2157299 monotherapy.

Additional exploratory analyses using proportional hazards models to control for other factors may be performed, including, but not limited to, adding a covariate indicating the extent of lomustine exposure, PD marker assessment of the tumor tissue, the known influence factors, such as age, PS, and primary or secondary GB and whether patients had poststudy treatment with bevacizumab.

The following secondary efficacy parameters will be summarized for each treatment group:

- PFS distribution parameters and PFS rate
- ORR
- Disease control rate

Progression-free survival (PFS) and PFS rate will be summarized (at **CCI** [REDACTED]) using Kaplan-Meier estimates of the median survival times (including 95% CIs) to inform assumptions for use in future trial planning (Kaplan and Meier 1958). Estimates of HRs

between the 3 arms will also be provided using proportional hazards models. Additional exploratory analyses using proportional hazards models to control for other factors may be performed.

Overall response rate (ORR) and, additionally, disease control rate given the risk of pseudoprogression, will be estimated by dividing the total number of responders ([CR or PR]) or [(CR or PR or SD)] by number of randomly assigned patients in each treatment group. Exact 95% CIs for each treatment arm will also be provided.

